## **Summary of Potential Adverse Events**

The table below outlines a series of possible adverse events that may be captured by the assessments within this study. These events will be monitored by the number of email triggers sent by the service during the study period.

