## **Type of Endpoint**

Efficacy/Safety: to measure the intervention's influence on help-seeking for depression, anxiety and stress; and to show that the intervention is safe under conditions of the proposed protocol.

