# **Trial Procedure**

Once parental consent is collected, the research team will visit the school to supervise participants' registration to the intervention (i.e. day one). The registration process will be completed online, during class time, using a computer/mobile/ or tablet device. Registration is estimated to take no more than 20-30 minutes. Although registration is completed privately by the student, a researcher or trained school staff member will be present to answer any questions and offer assistance. Baseline measures will be collected during this online registration process. Once all students have registered and completed the baseline assessment, a list of student names, alongside their trial identification numbers, will be given to the school counsellor. This will be used when the school counsellor is required to follow-up with a student as the email alerts do not contain student names (only the trial identification numbers). Throughout the trial, students will be able to use the intervention at their own leisure, either in or out of school time. Participants will also receive two optional monitoring questionnaires which are delivered via email (with SMS reminder) at day 15 and day 29. At day 43, a researcher will return to the school to collect the final endpoint measures using the same procedure for registration.

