## Procedure for responding to risk of significant harm within this Trial

Within the Smooth Sailing service, the pre-test and post-test assessments include the Patient Health Questionnaire (PHQ-9). This questionnaire is used to assess the presence of depression symptoms and has one item assessing suicidal risk (item 9). This item reads "Over the past two weeks, have you had any thoughts that you would be better off dead or of hurting yourself in some way". A participant is able to answer either 'not at all' (0); 'several days' (1), 'more than half the days' (2) or 'nearly every day' (3). The battery also includes the General Anxiety Disorder Questionnaire (GAD-7) which is used to screen for the presence of general anxiety symptoms. Both the PHQ-9 and GAD-7 are standardised psychological screening measures and as such, may provide an objective measure of anxiety, depression, and suicide risk if completed truthfully. However, further assessment from a trained mental health professional is required for the extent of an individual's risk to be fully determined. As such, the most appropriate response to elevated scores is to notify a trained mental health professional so that they can follow up with the participant. This is a commonly accepted protocol for mental health research studies. In the context of this study, the trained mental health professional will be the School Counsellor.

Given the sensitive nature of the questionnaires, students must be provided with adequate supervision for completion. In the current study, any student participating in the trial will be subject to the following supervisory conditions:

• Students will only be able to complete the questionnaires during class time, under the supervision of the researcher, school counsellor and/or class teacher. This will ensure that the student has adequate supervision, and if an alert is triggered, the school

- counsellor will be able to make timely contact. This will also ensure that the research team will be able to monitor the impacts of this questionnaire more precisely. Any student who cannot attend school for the class period in which the baseline and follow-up questionnaires are to be completed will not be able to participate in the study.
- A trained mental health researcher from the Black Dog Institute will be present at the
  school during class time for the completion of the baseline and follow-up

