  questionnaires. This researcher will supervise students during their completion of the
  questions, and monitor for distress. This researcher will verbally explain the process
  and provide instructions for what a student should do if feeling distressed (a. Let the
  researcher or the teacher know immediately by putting their hand up or asking to be
  excused). This researcher will have a valid WWCC which is included in the application.
- The school counsellor will also be onsite at the school and available for immediate contact for any students who require this during the completion of the baseline and follow-up questionnaires.
- A private breakout space (i.e. a classroom or school counsellor's office) will be made available should any student require private support.
- If a student reports that they are moderately severe or severely depressed/anxious during the baseline or follow-up questionnaires, then the school counsellor will be notified using the procedures outlined below under "Procedure for Responding to Risk of Significant Harm". The trial manager will also be notified and will follow-up with the school counsellor within 48 hours to ensure that the school counsellor is responding to the alert. Please note that the Trial Manager will be onsite for the completion of the baseline and follow-up questionnaires, and will therefore be able to check notifications immediately while participants are in the room. This allows for a swift response.
- To further support the school counsellor, a list of resources will be provided to the before the study commences, outlining additional adolescent mental health services that are available in their local area for referral. The Smooth Sailing Clinical Advisory Group (which consists of Child and Adolescent Psychiatrist and a Clinical Psychologist located at the Black Dog Institute) will also be available to provide any clinical support to the school counsellors wherever it is requested via telephone and email. This will ensure that the school counsellor feels adequately supported throughout the study, and increases the clinical capacity available to the students.

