**Table 1. Potential Adverse Events** 

Event	Assessment/Criteria	Action
"Moderately	A Patient Health	An automatic email alert will be sent to the
severe" or "severe"	Questionnaire-9 (PHQ-9)	nominated school counsellor and a member
depression at	baseline score of 15 or	of the research team. The school counsellor
baseline	above.	will be notified to follow-up with the
"Moderately	A Generalised Anxiety	participant using normal school protocols,
severe" or "severe"	Disorder (GAD-7)	including any mandatory reporting
anxiety at baseline	baseline score of 15 or	requirements. The trial manager will also re-
	above.	contact the school counsellor within 48

		hours to confirm that the email notification was received and is being acted upon. The research team will report to the outcomes advisory group at 2-week intervals on the total number of alerts.
Suicidal ideation at baseline	A score greater than or equal to one on the PHQ-9 item 9.	As above. In addition, a pop-up alert is shown to the participant which states the following: "Thanks for letting us know. We think it'd be great if you could tell a trusted adult about how you have been feeling. If you're not up to talking to someone you know, try Kids Helpline on [name] (it's not just for kids!) or Lifeline [name]. Smooth Sailing will let your School Counsellor know that it's been tough for you lately. Your School Counsellor will touch base with you in the next few days, just to see if there is anything they can do to help. Don't worry - this is all done very privately. In the meantime, keep using Smooth Sailing - we're here to help!"In addition, the participant will automatically receive access to the Smooth Sailing program which includes a range of psycho-education, help-seeking resources, and online therapy programs, which are evidence-based. Participants have access to this program for the duration of the trial.

Please see the supplementary material "Responding to risk of harm" document for a more detailed outline and flowcharts for decision making regarding risk of harm in the current trial.

Table 2 outlines additional adverse events during the trial which are not captured by the assessments and our action.

[figure not shown]

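### Every questionnaire-based adverse event is defined at baseline, before exposure, and reported only within an unsplit total of alert emails, which cannot support the stated safety aim

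*Protocol*

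**What the plan says.** Safety is a declared endpoint. Under Type of Endpoint, the protocol sets out "to show that the intervention is safe under conditions of the proposed protocol".

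The section Summary of Potential Adverse Events gives the metric for the events that the questionnaires capture: "These events will be monitored by the number of email triggers sent by the service during the study period". The table that follows (Table 1, Potential Adverse Events, not the earlier Table 1 on step allocation) lists three events, and each carries a baseline label:

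- depression, with a PHQ-9 criterion of "baseline score of 15 or" above;
- anxiety, with the same cut-off on the GAD-7;
- "Suicidal ideation at baseline", with the criterion "A score greater than or equal to one on the PHQ-9 item 9".

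The Outcomes Advisory Group receives the total number of alerts every two weeks. Table 2, Additional Adverse Events, covers events that reach the trial through the school. The counsellor passes these to the trial manager by phone or email, and the trial manager asks about them at six weeks. The report to the Advisory Group named in that table is again a total of trigger emails.

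The section on responding to risk of significant harm takes a wider view of timing. A student whose depression or anxiety score is moderately severe or severe "during the baseline or follow-up questionnaires, then the school counsellor will be notified". The paragraph after the table of care by step extends counsellor support to suicidal ideation reported at any time in the study.

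**The concern.** A baseline score is taken at registration, before the student is allocated to a step and before any tailored content is delivered. It describes illness that the student brought to the trial and cannot be an effect of the service. A safety endpoint needs what happened afterwards: who newly crossed a cut-off, who got worse, and what the school reported. The protocol defines no questionnaire-based event of that kind, although the PHQ-9 and GAD-7 are repeated at Day 43.

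The metric makes this harder to repair at the reporting stage. A count of emails has no denominator, does not count participants, and is not split by time point. Someone reading the total could not tell whether it reflects how ill the students were on Day 1, illness that persisted, or new illness.

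The count also carries weight in oversight. The protocol forgoes a data safety monitoring board partly because the platform has an alert system, and it admits students with current suicidality.

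**Working it through.** The protocol states no adverse-event rate, threshold or precision for safety, so there is no figure to reproduce. The check compares the sections and then sizes the problem from the protocol's own estimates.

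**1. Which time points count**

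| Section | Depression/anxiety at baseline | Depression/anxiety at Day 43 | Item 9 at baseline | Item 9 at Day 43 |
|---|---|---|---|---|
| Table 1, Potential Adverse Events | adverse event, alert | not defined | adverse event, alert | not defined |
| Responding to risk of significant harm (follow-up bullet) | alert | alert | not named | not named |
| Paragraph after the table of care by step | support | support | support | support |
| Summary of Potential Adverse Events | emails over the whole study period | same | same | same |

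Day 43 depression and anxiety alerts appear to be sent and could enter the email total, but they match no defined adverse event. For item 9 at Day 43 the sections do not settle whether an alert is sent at all. Events in Table 2, Additional Adverse Events, lie by definition outside the assessments, so nothing in the service would send an email for them and a total of trigger emails leaves them out.

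**2. Baseline events expected before exposure**

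Inputs: Step 3 share 10–15% and Step 4 share 5% (table of care by step); recruitment target 106 (Statistics). Steps 3 and 4 correspond to a PHQ-9 or GAD-7 of 15 or above.

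- Share at Steps 3–4: 10% + 5% = 15%, up to 15% + 5% = 20%.
- 106 × 0.15 = 15.9; 106 × 0.20 = 21.2.

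So about 16 to 21 participants meet the criterion before exposure. Those with item 9 of 1 or above but both totals below 15 come on top. The protocol gives no estimate of their number.

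**3. What an unchanged population would look like**

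The protocol plans for 64 participants after 40% dropout. Assume unchanged prevalence and dropout unrelated to severity: 64 × 0.15 = 9.6 and 64 × 0.20 = 12.8 would be at or above 15 at Day 43. The raw number falls from 16–21 to 10–13 although nobody's risk has changed.

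**4. What share of the total could be new onset**

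The protocol gives no rates for this, so the values here are assumptions for scale: persistence *p* of 30–70% among those at 15 or above at baseline, new onset *q* of 5–10% among the rest, and one alert per affected participant per time point. With baseline share *b*:

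- Day 43 alerts = 64 × [*b p* + (1 − *b*) *q*]. Lowest: 64 × (0.15 × 0.3 + 0.85 × 0.05) = 5.6. Highest: 64 × (0.20 × 0.7 + 0.80 × 0.10) = 14.1.
- New-onset alerts = 64 × (1 − *b*) *q*: from 64 × 0.80 × 0.05 = 2.6 to 64 × 0.85 × 0.10 = 5.4.
- New onset as a share of all alerts: from 2.6 / (21.2 + 11.5) = 8% to 5.4 / (15.9 + 8.3) = about 23%. With no new onset it is 0%.
- Baseline alerts as a share of all alerts: from 15.9 / (15.9 + 12.2) = 57% to 21.2 / (21.2 + 6.4) = 77%.

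Across these assumptions, most of the total is illness present before exposure.

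**5. What zero new-onset events would show**

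Completers at risk of newly reaching 15 are those below 15 on both scales at baseline: 64 × 0.80 = 51.2 to 64 × 0.85 = 54.4, about 51 to 54, if dropout is unrelated to severity. With zero events the one-sided 95% upper limit is 1 − 0.05^(1/n):

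- n = 51: 5.7%;
- n = 54: 5.4%.

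Using all 64 completers would give 4.6%, but that is the wrong denominator for new onset. The at-risk number for item 9 cannot be derived from the document.

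**The case against.** The strongest reply is that the trial does watch for harm after Day 1. Follow-up scores in the top two bands notify the counsellor and trial manager, triggers are counted over the whole study period, the school route covers suicide risk, low mood, anxiety and risk of significant harm, and the Day 43 PHQ-9 and GAD-7 are collected as outcomes. All of this stands. A reader might infer that worsening at Day 43 is missed or adds nothing to the count, or that a harmful and a helpful service would give the same number. The document does not support those readings, because follow-up alerts can enter the total.

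A second reply is that tables of n/N with confidence intervals belong in a statistical analysis plan, which is not at hand, and that the supplementary document on responding to risk of harm may settle follow-up alerts. This holds for the layout of tables and for alert handling. It does not reach the core of the point: the protocol itself fixes the event definitions at baseline and fixes the metric as a number of emails.

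A reader might also see a conflict between the rule "Students will only be able to complete the questionnaires during class time, under the supervision of the researcher" and the "two optional monitoring questionnaires which are delivered via email (with SMS reminder"). This is not pressed. In its context the class-time rule reads naturally as covering the baseline and follow-up battery, while the monitoring questionnaire is a separate, voluntary instrument.

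**Conclusion.** The point holds as a fault in the definition and counting of safety events, not as an absence of monitoring. Every questionnaire-based adverse event in the table is a pre-exposure state. The reported quantity is an unsplit email total in which baseline, persistent and new cases cannot be told apart, and from which school-reported events are absent. Worsening that stays below 15, or that starts from an already high score, is not identified by it.

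The size of about 16 to 21 of 106 rests only on the protocol's step estimates and recruitment target, and excludes participants who meet item 9 alone. The 8–23% share of new onset is illustrative and depends on the assumed persistence and onset rates. The limit of 5.4–5.7% depends on dropout being unrelated to severity.

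Followed as written, the plan would report pre-existing illness as adverse events and would have no defined count of new onset. With one arm and this sample, showing that the intervention is safe is more than the data can deliver. Nothing is lost for good, since the scores needed are already collected.

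**What to change.** 1. Reconcile the paragraph after the table of care by step, the follow-up bullet under responding to risk of significant harm, the Summary of Potential Adverse Events and its Table 1, so that they agree on which time points and which measures count as safety events, including item 9 at Day 43. No change of cut-off or clinical response is proposed here.
2. Report by participant and by time point, using the Day 1 and Day 43 data and the protocol's own cut-offs:
   - baseline alerts, listed as baseline characteristics;
   - new onset at Day 43 among those below the cut-off at baseline, separately for PHQ-9, GAD-7 and item 9, as n/N with 95% CI;
   - worsening of scores in all completers, which also picks up change below 15 and change from high scores;
   - school-reported events after Day 1, included in what the Advisory Group receives.
3. Reword the safety aim under Type of Endpoint as estimating the rate of new-onset or worsening events.

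The cost is protocol wording and one extra table, with no new data collection. The safety claim becomes more modest.

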**Table 1. Potential Adverse Events** 

Event	Assessment/Criteria	Action
"Moderately	A Patient Health	An automatic email alert will be sent to the
severe" or "severe"	Questionnaire-9 (PHQ-9)	nominated school counsellor and a member
depression at	baseline score of 15 or	of the research team. The school counsellor
baseline	above.	will be notified to follow-up with the
"Moderately	A Generalised Anxiety	participant using normal school protocols,
severe" or "severe"	Disorder (GAD-7)	including any mandatory reporting
anxiety at baseline	baseline score of 15 or	requirements. The trial manager will also re-
	above.	contact the school counsellor within 48

		hours to confirm that the email notification was received and is being acted upon. The research team will report to the outcomes advisory group at 2-week intervals on the total number of alerts.
Suicidal ideation at baseline	A score greater than or equal to one on the PHQ-9 item 9.	As above. In addition, a pop-up alert is shown to the participant which states the following: "Thanks for letting us know. We think it'd be great if you could tell a trusted adult about how you have been feeling. If you're not up to talking to someone you know, try Kids Helpline on [name] (it's not just for kids!) or Lifeline [name]. Smooth Sailing will let your School Counsellor know that it's been tough for you lately. Your School Counsellor will touch base with you in the next few days, just to see if there is anything they can do to help. Don't worry - this is all done very privately. In the meantime, keep using Smooth Sailing - we're here to help!"In addition, the participant will automatically receive access to the Smooth Sailing program which includes a range of psycho-education, help-seeking resources, and online therapy programs, which are evidence-based. Participants have access to this program for the duration of the trial.

Please see the supplementary material "Responding to risk of harm" document for a more detailed outline and flowcharts for decision making regarding risk of harm in the current trial.

Table 2 outlines additional adverse events during the trial which are not captured by the assessments and our action.

[figure not shown]

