- 3. Delivery of tailored program. After step allocation, Smooth Sailing delivers a program of content that is tailored to each step. Steps 0 and 1 receive online psychoeducation. Step 2 receive online psychoeducation + online self-directed Cognitive Behavioural Therapy (CBT). Steps 3 and 4 receive online psychoeducation + online self-directed CBT + additional support from the School Counsellor. Any participant who was allocated to Step 3 or 4 triggered an electronic notification alert which was automatically sent to the school counsellor for further investigation. This allowed the school counsellor to facilitate a face-to-face session within 48 hours to provide the counselling or refer on to external services. The online psychoeducation consists of five modules on i) general mental health, ii) depression, iii) anxiety, iiii) seeking help for yourself, iv) seeking help for a friend. Each of these modules contains information about definitions of mental health terms, signs and symptoms, causes of mental health problems, what to do if needing help, and strategies and tips for what a young person can do immediately. Each module is complemented by animations and illustrations to depict key messages as well as hyperlinks to other credible youth mental health services and websites including Headspace, Reachout, Kids Helpline. This content was created specifically for this service, and was reviewed by clinicians. It is designed to be self-directed, such that the youth can read and return to it whenever they wish. The online CBT module consists of a single webpage that outlines two evidence-based self-directed online cognitive behavioural therapy programs: i) MoodGym (Australian National University) and ii) Brave Online (University of Queensland). MoodGym is an interactive self-help book which helps to learn and practise skills for managing symptoms of depression and anxiety. It consists of five modules alongside questionnaires, summaries and a personal workbook. BRAVE was developed for children and teenagers who experience Separation Anxiety Disorder, Social Phobia, Specific Phobia and Generalised Anxiety Disorder. This program helps young people to learn new ways to manage their anxiety and fears. It consists of 10 sessions and is effective for reducing social worries, anxiety about separating from loved ones, fears of specific objects or situation, worries about friendships, school performance or other everyday worries. Please see Table 2 for more detail.

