- 4. Monitoring and Feedback. At two points in the study (Day 15 and Day 22) participants received an automated 18-item "monitoring questionnaire" to assess how they were doing. This consisted of the Goldberg Depression and Anxiety Scales and was delivered via email or SMS. An automated thank you message was received alongside a reminder to use the program if participants completed this questionnaire.
- 5. Reassessment (Post-test/endpoint): At Day 43, researchers revisited the schools. Participants again logged onto the service using the same URL and unique ID codes and were delivered the final endpoint questionnaires. In theory, the results of these questionnaires would be used to determine whether a participant had responded to care or needed to be "stepped up". In accordance with the Clinical Practice Guidelines for the Treatment of Depression in Young Adults, if a participant has not responded to their care within 43 days of their baseline allocation, they would be "stepped up" to the next level of care. See Table 3 below for the stepping matrix at 43 days. The matrix was designed such that a participant would not be stepped down, instead will either remain at the same step or step up. However, as the current trial ceased at 43 days, no stepping occurred during this trial. Instead, this trial was

designed to provide the clinical data necessary to determine whether the steps are feasible for future trials.

Throughout the trial, participants will be obligated to use Smooth Sailing at pre-test (for registration and baseline measure collection) and again at post-test (for reassessment and final endpoint collection) only. Completion of the monitoring questionnaires and use of the other components is entirely voluntary, and will be a measured as part of the study.

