**Table 1. Step Allocation Criteria** 

Step	Severity Level	Criteria
Step 0 &	Nil, minimal	PHQ9 (0 - 4) & GAD7 (0 - 4)
Step 1	Mild	PHQ9 (5 - 9) & GAD7 (0 - 9)
		OR
		PHQ9 (0 - 9) & GAD7 (5 - 9)
Step 2	Moderate	PHQ9: (0-14) & GAD7: (10-14)
		O R
		PHQ9: (10-14) & GAD7: (0-14)
Step 3	Moderately	PHQ9: (0-19) & GAD7:(15-19)
	Severe	OR
		PHQ9: (15-19) & GAD7: (0-19)
Step 4	Severe	PHQ9: (0-27) & GAD7: (20-21)
		O R
		PHQ9: (20-27) & GAD7: (0-21)

Table 2. Care delivered at each step

Step	Severity Level	Care provided
Step 0 and 1	Nil, minimal, mild	Online psycho-education: This consists of written text, videos, and activities created by Black Dog Institute researchers. It also includes URL links to other psycho-education material published by reputable Australian mental health organisations including headspace, Reachout, beyondblue and SANE Australia. It is estimated that 60% of participants will be allocated to this step at baseline.
Step 2	Moderate	Self-directed online cognitive behavioural therapy (CBT) in addition to the online psycho-education material. The online CBT programs that will be offered by Smooth Sailing are evidence-based, produced by Australian university research groups, and free to access. The programs include MoodGym (Australian National University), and Brave Online (University of Queensland). It is estimated that up to 25% of participants will be allocated to this step at baseline.
Step 3	Moderately Severe	Self-directed online cognitive behavioural therapy (CBT) in addition to the online psycho-education material and additional support from the school counsellor. This support will be offered face-to-face by a school counsellor. In the current study, any participant who reports moderate symptoms will trigger an electronic notification alert which will be automatically sent to the school counsellor or head teacher for further investigation. This will allow the school counsellor to facilitate a face-to-face session to provide the

		counselling or refer on to external services. It is estimated that between 10-15% of participants will be allocated to this step at baseline.

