Step 4	Severe	Self-directed online cognitive behavioural therapy (CBT) in addition to the online psycho-education material and additional support from the school counsellor. In the current study, any participant who reports moderate symptoms will trigger an electronic notification alert which will be automatically sent to the school counsellor or head teacher for further investigation. This will allow the school counsellor to facilitate a face-to-face session to provide the counselling or refer on to external services. It is estimated that 5% of participants will be allocated to this step at baseline.

Throughout the trial, the school counsellor will be physically located within the school that the participant attends. He or she has a background in counselling or psychology and is present at the school at least two days per week. The school counsellor will provide clinical support to any participant that reports moderately severe or severe depression/anxiety scores, or reports suicidal ideation throughout the study. See Assessment of Efficacy for details on how service use, adherence, and satisfaction will be measured.

Table 3. Step Allocations at Day 43 based on Step at Baseline

	Step at Baseline	1	2	3	4
Step at 43 days					
1		1	2	3	4
2		2	3	3	4
3		3	3	4	4
4		4	4	4	4

Comparator: No control group as it is an uncontrolled trial.

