#### Post-test/Final endpoint Assessment

At day 43, participants will return to the website to complete the online battery of questionnaires including the: Patient Health Questionnaire (PHQ-9); Generalised Anxiety Disorder Questionnaire (GAD-7); the General Help Seeking Behaviour Questionnaire and Actual Help-seeking Behaviour Questionnaire and the Satisfaction Questionnaire for Students Acceptability and demand measured by: The number of youth and parents who consented to the study; The number of modules completed; The number of students who reported using the online CBT programs; The number of students who completed the fortnightly check-in questionnaires;

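### No written alert rule covers a positive PHQ-9 suicidal-ideation answer at Day 43 when both symptom totals are below 15

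*Protocol*

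**What the plan says.** The PHQ-9, including item 9 scored 0 to 3, is completed at pre-test and at Day 43 (Protocol, Post-test/Final endpoint Assessment; Procedure for responding to risk of significant harm within this Trial).

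The protocol states what should follow from a worrying answer in several places:

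- **Table 1, Potential Adverse Events.** The row headed "Suicidal ideation at baseline" sets the criterion at 1 or more on item 9. It leads to an email to the counsellor and research team, a 48-hour check by the trial manager, and an on-screen message to the student.
- **Procedure for responding to risk of significant harm.** If a student is "moderately severe or severely depressed/anxious during the baseline or follow-up questionnaires, then the school counsellor will be notified". The same section says that "the most appropriate response to elevated scores is to notify a trained mental health professional", and names the school counsellor as that professional.
- **Intervention, delivery of tailored program.** "Any participant who was allocated to Step 3 or 4 triggered an electronic notification alert" to the school counsellor.
- **Intervention, paragraph after Table 2 (Care delivered at each step).** The counsellor supports any participant with moderately severe or severe scores "or reports suicidal ideation throughout the study".

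**The concern.** The protocol commits to acting on suicidal ideation for the whole study, but its only rule that turns an item 9 answer into an alert is labelled for baseline. This is an inconsistency in the text. It does not show that the platform's alert was switched off at Day 43, and baseline coverage is not in question.

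Three features of the trial make it matter:

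- Day 43 is the last scheduled assessment and gives the only item 9 answer after students have had access to the program. No later assessment can catch a miss.
- The Inclusion Criteria admit adolescents with current suicidality, so positive answers are foreseeable, and the Type of Endpoint section names safety.
- The Summary of Potential Adverse Events monitors the tabulated events by counting email triggers, so ideation that raises no email is absent from that count. The alert system is also one of two reasons the Outcomes Advisory Group section gives for having no data safety monitoring board.

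**Working it through.** The protocol gives no figure to reproduce. The check has two parts: whether any written rule reaches the case, and whether the case can occur.

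**1. Each rule against the case: Day 43, item 9 of 1 or more, both totals below 15**

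| Rule | Time point | Criterion | Reaches the case? |
|---|---|---|---|
| Table 1, Potential Adverse Events: ideation row | Baseline (row heading) | Item 9 of 1 or more | No, by its heading |
| Same table: depression and anxiety rows | Baseline | PHQ-9 or GAD-7 of 15 or more | No |
| Procedure for responding to risk: notification bullet | Baseline or follow-up | Moderately severe or severe, i.e. 15 or more | No, item 9 is not mentioned |
| Intervention: step alert | On step allocation | Step 3 or 4, set from totals in Table 1, Step Allocation Criteria | No. The section adds that "as the current trial ceased at 43 days, no stepping occurred during this trial" |
| Table 2, Care delivered at each step (rows for Steps 3 and 4) | Not stated | "any participant who reports moderate symptoms will trigger an electronic notification alert" | Not for totals below 10, even on the loosest reading |
| Table 2, Additional Adverse Events | During trial | Reported to, or identified by, the school | No. The table is introduced as covering what the assessments miss |
| Outcomes Advisory Group: alert system | Not stated | None given | No criterion to apply |

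The commitment to support ideation throughout the study, and the duty-of-care section that counts reported suicidal thoughts as risk of significant harm, state an obligation. Neither gives a threshold that would notify anyone of an online answer at Day 43.

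**2. Can the case occur?**

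Inputs: item 9 is scored 0 to 3 (Procedure for responding to risk); the PHQ-9 total runs to 27 and the step bands end at 4, 9 and 14 (Table 1, Step Allocation Criteria).

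If item 9 = k and the total is at most T, the other eight items may sum to at most T − k.

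| Upper limit T | k = 1 | k = 2 | k = 3 |
|---|---|---|---|
| 14 (below the alert level) | 14 − 1 = 13 | 14 − 2 = 12 | 14 − 3 = 11 |
| 9 (below moderate) | 9 − 1 = 8 | 9 − 2 = 7 | 9 − 3 = 6 |
| 4 (nil/minimal) | 4 − 1 = 3 | 4 − 2 = 2 | 4 − 3 = 1 |

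Every entry is at least 0, so each positive item 9 score fits each band. A student with the highest item 9 answer and zeros elsewhere totals 3. With a GAD-7 of 0–4, that student falls in the Step 0 band, where care is online psychoeducation only.

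**3. Coverage**

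Item 9 administrations: 2. With a written item 9 trigger: 1 (baseline). Without one: 2 − 1 = 1 (Day 43). No endorsement rate is assumed, because the protocol gives none.

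**The case against.** The strongest reply is that the protocol already instructs notification at both time points. The risk procedure says the PHQ-9 is used before and after, singles out item 9 as the suicide-risk item, and concludes that elevated scores should go to the counsellor. On this view only a repeated cut-off is missing. The baseline label is also weak evidence of a restriction: the ideation criterion itself does not mention baseline, and the follow-up notification bullet shows that the neighbouring rows are not meant to stop there. Finally, the protocol refers to a supplementary document with decision flowcharts on risk of harm. That document was not available, nor was a figure placed after the table.

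Much of this stands. The intent to respond is clear, a drafting slip is the likelier reading, and the supplement may contain the rule. But the general sentence does not say what counts as elevated on item 9 at follow-up, and the one bullet that puts it into practice at follow-up uses symptom severity alone. It corrects the baseline label for depression and anxiety and leaves ideation uncorrected.

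The on-site arrangements also count for something. A researcher watches for distress, the counsellor is available, the trial manager can check notifications while students are in the room, and the counsellor is asked about adverse events at six weeks. These rely on visible distress, on a student speaking up, or on an alert having fired. None detects a private answer that raised no alert.

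**Conclusion.** The concern holds as a statement about the protocol's text. A student with item 9 of 1 to 3 and both totals below 15 at Day 43 meets no written criterion for the email alert, pop-up or 48-hour check, despite the commitment to support ideation throughout the study. The gap covers one of two item 9 administrations, the only one after exposure, and can arise at any positive item 9 score.

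The number of students affected cannot be derived. The conclusion assumes that the row heading is taken literally and that no rule outside this document fills the gap. Confidence is medium for those reasons. The primary outcome, analysis and sample size are unaffected. The change should be made because, followed as written, the rules could leave a reported suicidal thought without notification.

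**What to change.** 1. In Table 1 (Potential Adverse Events), make the three row headings read baseline or Day 43, and remove the word baseline from the two score criteria.
2. In the risk procedure, add a score of 1 or more on PHQ-9 item 9 to the bullet that governs notification at baseline and follow-up.
3. Run the existing email alert, pop-up and 48-hour check at Day 43. Edit the pop-up's closing advice to go on using the service, since access lasts only for the trial.
4. State that Day 43 alerts are included in the count reported to the Outcomes Advisory Group.

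If the supplementary document already sets the Day 43 trigger, only the wording in items 1 and 2 is needed, so that the two documents agree. If Day 43 has already passed, compare the alert log with the Day 43 item 9 answers, state which rule was run, and tell the counsellor of any answer of 1 or more that raised no alert.

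The cost is wording in two places and an existing alert applied at a second time point. There are no extra assessments. The downside is a few additional counsellor follow-ups after the final visit.
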